## **SUMMARY**

The subcrestal placement implant has a positive impact on papilla formation and allows an emergence profile suitable for an aesthetic restoration. Its placement allows the implant-abutment interface to be in a position that contributes to bone remodeling in the neck region of the implant, compared to implants placed at bone level (bone-level,crestal placement). Marginal bone loss from implants placedcrestal or subcrestal has shown conflicting results in recent studies.

## **1.- BACKGROUND OF THE SUBJECT**

Dental implants have been introduced as an option for replacing missing teeth, since the initial studies of [name] in the 1950s, there are multiple studies that support it, including (Andersson B, 1995; Arlin M, 1993; Noack et al, 1999; Jemt T, 2017; The accepted criteria for evaluating implant success were proposed by Albrektsson et al. (Albrektsson et al, 1986), who to identify clinical evidence of successful osseointegration and implant survival, suggested that a marginal bone loss of less than 1.5 mm in the first year and 0.2 mm in the following years, it is acceptable after implant loading (Díaz-Sánchez et al, 2019). Over the past three decades, implant success has been evaluated by survival rates, prosthesis stability, radiographic bone loss, and the absence of infection in the peri-implant soft tissues (Albrektsson et al, 1986; Smith and Zarb 1989; Buser et al, 1990, Albrektsson and Zarb 1998, Misch et al, 2008; The progressive knowledge of patients has increasingly required treatments that offer better aesthetics and comfort, making implantology a demanding field, where obtaining osseointegration or meeting the success criteria of implants highlighted by the lack of pain and infection, absence of radiolucency and mobility and possibility of restoration (Buser et al, in the 1990s). Thus, new parameters have been introduced to evaluate the long-term success of implant restorations. Including health status and natural-looking peri-implant soft tissues, prosthodontic parameters, aesthetics and patient satisfaction. However, osseointegration remains the predominant parameter in implantology (Furhauser et al, 2005; Meijer et al, 2005; Annibali et al, 2009; Belser et al, 2009).

Various authors describe that the position of the implant with respect to the crestal bone is a fundamental factor to preserve the bone in the future (Pontes et al, 2008; Novaes et al, 2009; De Siqueira et al, 2017; Wennerberb et al. al, 2003; Although, regarding this issue there continues to be controversy. Thus, some authors recommend placing the

implant below the crest of the bone (i.e., subcrestal placement). They argue that this position will contribute to the preservation of the mucosa (Pontes et al, 2008), helping to obtain an ideal emergence profile in aesthetic areas (Novaes et al, 2009; Di Siqueira et al, 2017) and preventing the surface of the implant is exposed; at the same time that the presence of mucositis or peri-implantitis is reduced (Wennerberg et, 2003). A possible reason for this could be bacterial colonization of the implant-abutment junction, where an inflammatory infiltrate occurs (Do-Nascimento et al, 2012; Hermann et al, 2000; Broggini et al, 2003). This characteristic, in conjunction with a low oxygen concentration, could create an ideal ecosystem for the proliferation of anaerobic bacteria (Piattelli et al, 2003). On the other hand, it could be speculated that deeper implant placement may correlate with deeper pockets and soft tissue inflammation (Siqueira et al, 2017).

In another order of things, the connection of the implant with the abutment involves microspaces. These microspaces (which facilitate the accumulation of bacteria) can influence peri-implant bone resorption along with other factors such as surgical trauma, the establishment of the biological width, the design of the implant and the position of the implant (Palacios-Garzón et al, 2019 ; Díaz-Sánchez, et al, 2019; Buser et al., 1990). Studies have shown that this microgap varies between 0 and 135 µm (Dellow et al, 1997; Callan et al, 1998). However, what deserves special attention is that, as in teeth, the biological width is formed around the implants, consisting of a junctional epithelium and connective tissue with an average dimension of approximately 2 mm and 1–1.5 mm, respectively (Berglundh et al, 1991). On the other hand, different risk factors can affect implant lifespan, such as anatomical characteristics, chewing dynamics, and proper implant selection, which are important for long-term prognosis. Today, we know that implants with rough surfaces show a statistically higher survival rate than machined implants at all intervals (Levin et al, 2006).

Maintaining the level of the crestal bone around dental implants is essential for their long-term success and survival (Mei et al, 2017; Al Amri et al, 2017; Marcelo-Machado, et al 2018). Factors that may showcrestal bone resorption in dental implants that affect the survival rate of the dental implant, such as the amount of overload stress (Stoichkov et al, 2018), micromotion (King et al, 2002), location and bacterial infiltration of the implant-abutment connection (Blanco et al, 2008; Kozlovsky et al, 2007; Tripodi et al, 2015), periodontal phenotype (Linkevicius et al, 2010), bone density (Hermann et al, 2001; Goiato et al, 2014), trauma surgical (Canullo et al, 2012) and maintenance of oral hygiene (Kozlovsky et al, 20007). In the actulaida, several treatment protocols have been proposed to reduce marginal bone loss around implants (Calvo-Guirado et al, 2015; Vohara et al, 2015; Romanos et al, 2014), including implant placement by below the level of the bony crest (subcrestal placement) (Kutan et al, 2015). Furthermore, the subcrestal implant also has a positive impact on papilla formation and allows for an adequate emergence profile for better aesthetic restoration (Vela-Nebot et al, 2006; Koutouzis et al, 2014). In this placement the implant-abutment interface is in a position that contributes to bone remodeling in the neck region of the implant compared to implants placed at bone level (crestal placement) (Outouzis et al, 2011; Charalampakis et al, 2014). On the other hand,

marginal bone loss from subcrestal implants compared to crests has shown contradictory results in recent studies (Gale et al 2013). Thus, some studies reported similar bone levels for both implant placement techniques (Casagrande et al, 2020). Therefore, we believe it is necessary to continue researching in this field, to make decision-making easier for the clinician.

## **2-JUSTIFICATION**

Various treatment protocols have been proposed to reduce marginal bone loss around implants, including placement of implants below the level of the bone crest (subcrestal placement). The supracrestal implant also has a positive impact on papilla formation and allows an emergence profile suitable for an aesthetic restoration. Allowing the implant-abutment interface to be in a position that contributes to bone remodeling in the implant neck region compared to implants placed at bone level (crestal placement). Marginal bone loss from implants placed bestially/subcrestally has shown conflicting results in recent studies. In this study we intend to evaluate bone loss in 100 Tissue level implants from two different commercial companies: Straumann bone level® with the Bio horizon Tissue level® implant. Buying the data obtained with the existing literature.

## **3- HYPOTHESIS**

### **3.1- Main hypothesis**

#### **Null hypothesis:**

Two different brands of implants behave in the same way in terms of marginal bone loss, if they are placed based on the indications specified by the manufacturer.

#### **Alternative hypothesis:**

Two different brands of implants behave in the same way in terms of marginal bone loss, if they are placed based on the indications specified by the manufacturer.:

## **3- HYPOTHESIS**

### **3.1- Main hypothesis**

**Null hypothesis:** A brand of implant behaves in the same way in terms of marginal bone loss, if it is placed according to the indications specified by the manufacturer (crestal level or supracrestal level).

### **Alternative hypothesis:**

A brand of implant does not behave in the same way in terms of marginal bone loss, if it is placed according to the indications specified by the manufacturer (crestal level or supracemental level).

## **4-OBJECTIVES**

### **4.1 Main objective:**

To evaluate marginal bone loss in two different brands of implants placed at the bone level.

### **4.2 Secondary objectives:**

- Relationship between marginal bone loss and suprabony soft tissue in mm.
- Relationship between marginal bone loss and ISQ value at the time of implantation.
- Relationship between marginal bone loss and torque (in Newton) at the time of implantation.
- Relationship between marginal bone loss and implant location.
- Relationship between marginal bone loss and the degree of periodontal disease.
- Relationship between marginal bone loss and systemic diseases.
- Relationship between marginal bone loss and smoking

## **5- MATERIAL AND METHOD**

### **5.1- Study design**

It is a prospective clinical study to compare two implants from two different brands of a similar design for their implantation [tissue level] and to evaluate the marginal bone loss of each dental implant in mm. 96 patients will be analyzed (an expected N of 48 per group, hoping to reach at least 100 implants per arm). See calculation of N in point 5.7.

### **5.2- Study population**

The patients will be collected from patients who attend the master's degree in medicine, surgery and Oral Implantology, requesting implant-supported treatment. The study population will consist of patients who require treatment with dental implants, either partially or completely edentulous and who accept their placement and participation in the study. 4.2.1 Inclusion / exclusion criteria

### **5.3-Inclusion/exclusion criteria**

#### ***Inclusion:***

- Patients of both sexes, over 18 years of age, who need dental implant placement for prosthetic rehabilitation. Whether partially or completely in both the maxilla and the mandible.

- Patients with residual alveolar ridge with at least 8 mm of bone height and 4 mm of width.
- Patients must have the ability to understand and decide at the time of voluntarily signing the informed consent before carrying out any intervention related to the study.
- Patients who, after being informed about the objectives and procedures of the research, agree, will sign the informed consent form. And they are ready to carry out the different study visits.

***Exclusion:***

- Patients with uncontrolled systemic diseases (ASA  $\geq$  III).
- Patients who do not have 8mm bone height and/or 4mm width
- Patients who require bone regeneration
- Patients with severe periodontal disease or acute pericoronitis.
- Pregnant and breastfeeding women.
- Patients with Deficient or Inadequate Oral Hygiene.
- Patients with severe bruxism.
- Patients taking bisphosphonates or other antiresorptive medications.
- Smoker of more than 10 cigarettes/day.
- Patients with uncontrolled diabetes mellitus.
- Psychiatric illnesses or unrealistic expectations.
- Immunocompromised or immunosuppressed patient.

**5.4.-Recruitment**

The sample will be for convenience and will be obtained from patients of the Hospital Odontològic Universitat de Barcelona (Houb) who come to the service of the Master of Dentistry in Oral Medicine, Surgery and Implantology. Once the protocol is approved by the Ethics and Research Committee with Medicines and Health Products of the same Houb (CEIm-Houb), the recruitment of study participants will begin, estimated to take one year and 2 months, starting in November 2022.

**5.5.- Procedures**

**5.5.1 First session and recruitment**

In this first session, before starting surgery and prosthodontic treatment, a thorough medical history will be taken. Each patient will be examined by extra-oral and intra-oral examination, in addition to the evaluation of their respective orthopantomography and cone beam computed tomography (CBCT), to evaluate the level of height and width of the bone for the placement of dental implants. This process will be carried out by the main researcher and supervised by another expert in Dentistry. Study participants who meet the inclusion criteria will then be recruited and asked if they wish to participate. Each of them will be given the following records.

If the patient meets the criteria and is interested, they will sign the informed consent and will be randomized using a randomization table of 10 in 10 implants [e.g.: randomization table ABBAABBBAB] to place one type or another of implant:

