### 5.5.2 Second session

The patient will come to the Hospital for primary impressions with alginate. Then a cast will be made with gypsum for study the case and bite of the patient will be taken with wax to record it.

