### 5.5.3 Third session

The patient will come to the Hospital to operate the surgery within 15-20 days after having the study cast revised by a dentist and specialist from the fixed department. The patient will have a temporary prosthesis (Fixed or Removable) after the surgery of the implant. A periapical X-Ray will be taken immediately after the surgery to control the marginal bone loss. With respect to accepted criteria for the assessment of implant success were proposed by Albrektsson and colleagues (Albrektsson *et al.*, 1986), which to identify clinical evidence of successful osseointegration and survival of implants, suggested that a marginal bone loss of less than 1.5 mm in the first year and 0.2 mm in the following years is acceptable after implant loading.

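### The brand is drawn before the study cast is made and reviewed, and neither the sites nor the number of implants is fixed first, so both can depend on the allocated brand

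*Protocol*

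**What the plan says.** Section 5.5.1 puts the history, the extra- and intra-oral examination, the orthopantomography and the CBCT in the first session. The imaging serves "to evaluate the level of height and width of the bone for the placement of dental implants". Then, "If the patient meets the criteria and is interested", "they will sign the informed consent and will be randomized using a randomization table"; the table runs in tens of implants.

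Section 5.5.2 places the impressions in the second session: "Then a cast will be made with gypsum for study the case". Section 5.5.3 places surgery in the third session, "within 15-20 days after having the study cast revised by a dentist and specialist from the fixed department".

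Section 5.1 gives the planned size as "an expected N of 48 per group, hoping to reach at least 100 implants per arm" and states that marginal bone loss is evaluated for each implant. Section 5.7 counts its subjects as implants. Section 5.8 compares bone loss with a t-test and a multiple linear regression on implant type. The control variables it names are sex, age, smoking, jaw, ISQ and mesial and distal neighbours.

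**The concern.** Randomisation makes the arms comparable in whatever is fixed before the draw. Here the draw fixes who is in each arm, but not which implants each patient contributes. Those who study the cast and settle the prosthetic plan may already know the brand. If that knowledge influences how many implants are planned, or where, the arms can differ in the implants they supply even though the patients were balanced.

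The main objective is a comparison of marginal bone loss between brands. A difference in case mix created after allocation would enter that comparison directly. More patients would not remove it.

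**Working it through.** **1. The plan's own figure.** Inputs from section 5.7: difference 0.2 mm, SD 0.34, two-sided alpha 0.05, power 0.80, loss 5%.

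- n per group = 2 × [0.34 × (1.960 + 0.842) / 0.2]² = 45.4.
- Allowing for loss: 45.4 / 0.95 = 47.8, so 48.

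The stated 48 per group is reproduced. It does not bear on the order of events.

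**2. The order of events.**

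| Session | Step | Relative to the draw |
|---|---|---|
| First (5.5.1) | History, examination, orthopantomography, CBCT, eligibility check, consent | Before |
| First (5.5.1) | Draw of the brand | – |
| Second (5.5.2) | Impressions, study cast, bite record | After |
| Before the third (5.5.3) | Cast reviewed by a dentist and the fixed-prosthesis specialist | After |
| Third (5.5.3) | Surgery, within 15-20 days of that review | After |

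No step before the draw records the planned sites, number of implants or prosthesis type. No step after it conceals the brand from the planners.

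**3. How open the number of implants is.** Section 5.1 gives 48 patients and at least 100 implants per arm.

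- 100 / 48 = 2.08 implants per patient.
- If each of the 48 patients receives at least one, 100 − 48 = 52 of 100 implants are additional to the first. More than half of the implant-level data thus depends on how many implants each plan calls for.

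**4. Why this matters at implant level.** Let patient i have m_i implants with mean bone loss y_i. The implant-level mean of an arm is

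Σ m_i y_i / Σ m_i = ȳ + Cov(m, y) / m̄,

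where ȳ is the unweighted patient mean and m̄ the mean number of implants. The difference between arms therefore contains the term

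Cov_A(m, y) / m̄_A − Cov_B(m, y) / m̄_B.

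If the number and sites are set before the draw, this term has no systematic source other than an effect of the brand on bone loss itself. If they are set with the brand known, the term can differ between arms although the two implants behave alike, and a brand-dependent choice of sites can shift ȳ itself. The protocol supplies m̄ (about 2.08 as a target) but neither the covariance nor any brand effect on planning, so the term cannot be evaluated.

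**5. Whether the regression repairs it.** Jaw and neighbouring contacts capture part of the choice of site. The number of implants and the ridge dimensions are not among the variables named in section 5.8. ISQ is the named variable closest to bone quality, but section 4.2 takes it at implantation, after allocation, so it may itself depend on the brand.

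**6. The unit of the table.** Section 5.5.1 says patients are randomised, yet counts the table in implants. If implants are the unit, each patient's number must be known at the first session, and the protocol does not say that it is recorded then. If patients are the unit, the number stays open after the draw. Under either reading, no recorded plan precedes the allocation.

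**The case against.** The strongest reply is that much of the planning may already be done at the draw. CBCT and orthopantomography come first, and randomisation is conditional on meeting the criteria. The Economic report prices CBCT for a quadrant or for a single implant depending on the case, which suggests that the intended region is roughly known when imaging is ordered. Sections 5.5.2 and 5.5.3 do not say that sites or numbers are decided at those steps. Section 5.1 calls the two implants similar in design.

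This stands in part. A reader might infer from the sequence that the brand is drawn before the case is studied at all; section 5.5.1 contradicts that. But a bone assessment is not a recorded plan. A cast made to study the case, then reviewed by a prosthetic specialist, leaves room to change the number and sites.

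A reader might also infer that patients found at surgery to need regeneration would be dropped, and unequally by brand, because the exclusion list contains "Patients who require bone regeneration". The protocol does not support this. The item is an eligibility criterion to be met before randomisation, no section provides for exclusion during surgery, and nothing shows that the need would differ by brand.

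Finally, the handling of deviations after randomisation is commonly left to the SAP, so silence on it is no fault here. The timing of the draw is different: it is trial conduct, which this protocol sets and an analysis plan cannot move.

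**Conclusion.** The point holds in a limited form. The protocol draws the brand after CBCT and the eligibility check but before the cast is made and reviewed. It leaves the number of implants open and compares bone loss at implant level. It neither fixes sites and number before the draw nor conceals the brand from the planners, so sites and numbers can depend on the brand.

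The document does not show that planning would in fact differ by brand. The size of any bias cannot be derived from it: a figure would need an assumed effect of the brand on planning and an assumed link between planning and bone loss, and the protocol gives neither. This is an avoidable route to bias in the main comparison, not a demonstrated bias. It should be closed because closing it is cheap.

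**What to change.** Revise sections 5.5.1 to 5.5.3 as follows:

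- Keep consent at the first session and remove the draw from it.
- After the cast review, record the planned number of implants, their sites and the prosthesis type in a dated entry.
- Re-confirm the existing eligibility criteria.
- Only then open the allocation, as close to surgery as feasible.
- State that every randomised patient is analysed in the assigned arm.
- State in the same revision whether the table allocates patients or implants, since moving the draw does not settle that by itself.

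The cost is protocol wording and one recorded entry per patient. Both implant systems must be available at surgery. No extra visit, procedure or patient is needed.

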### 5.7.- Sample calculation

According to data obtained in the study by Natalia Palacios-Garzon et al, 2020 (taking into account that both are internally connected implants), in order to detect changes of 0.2mm we would need: Accepting an alpha risk of 0.05 and a beta risk of 0.2 in a bilateral contrast, 48 subjects (implants) in the first group and 48 (Implants) in the second are needed to detect a difference equal to or greater than 0.2 units.

The common standard deviation is assumed to be 0.34. A loss to follow-up rate of 5% has been estimated.

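### The allocation table in Protocol 5.5.1, illustrated by a ten with 4 A and 6 B, does not secure the planned 48 per group and leaves block structure, unit and list custody open

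*Protocol*

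**What the plan says.** Protocol 5.5.1 fixes an allocation method. After eligibility is checked and consent signed, the patient is "randomized using a randomization table of 10 in 10 implants [e.g.: randomization table ABBAABBBAB". The eligibility work-up takes place in the same session: "This process will be carried out by the main researcher and supervised by another expert in Dentistry". The section does not say how the table is generated, who keeps it, or whether those who enrol patients can see it. Section 5.4 describes recruitment at one hospital, and no masking is described.

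The sizes that this table must deliver are given twice. Section 5.1 states: "96 patients will be analyzed (an expected N of 48 per group, hoping to reach at least 100 implants per arm". Section 5.7 states: "48 subjects (implants) in the first group and 48 (Implants) in the second are needed". Both imply 1:1 allocation. They count different things: patients in 5.1, and subjects glossed as implants in 5.7. The table in 5.5.1 is itself counted in implants, although the sentence around it randomises the patient.

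**The concern.** The usual reason to work a randomisation table in tens is to keep the arms level after each ten. The only ten shown does not do so. The example and the 1:1 plan therefore disagree, and the text does not say which kind of table is meant.

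Two things are at stake. The smaller is balance and the power that goes with it. The larger is concealment. If upcoming allocations can be seen or inferred, whoever decides on enrolment can, knowingly or not, match patients to brands. Some exclusions in 5.3, such as inadequate oral hygiene, severe bruxism or unrealistic expectations, leave room for judgement, and the sample is one of convenience. The target difference is only 0.2 mm, so modest steering could matter.

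The unit matters as well. At 100 implants per arm and 48 patients per arm, a patient receives on average 100/48 = 2.1 implants, so a ten counted in implants covers about 10/2.1 = 4.8 patients. If each patient receives one brand throughout, the sequence cannot be followed implant by implant. If each implant follows its own letter, some patients receive both brands. The protocol does not say which applies.

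**Working it through.** **Inputs.** From 5.7: two-sided alpha 0.05, power 0.80, difference 0.2 mm, SD 0.34, loss 5%. From 5.1: 96 patients, 48 per group. From 5.5.1: the string ABBAABBBAB. Units are treated as independent throughout.

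**The plan's own figure.** n = 2(z₀.₉₇₅ + z₀.₈₀)²σ²/δ² = 2 × (1.960 + 0.842)² × 0.34²/0.2² = 45.37 per arm, and 45.37/0.95 = 47.8, so 48. (Rounding to 46 first gives 49; the t-based version gives 47, or 50 after loss.) The 48 is reproduced and assumes equal arms.

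**The example.** ABBAABBBAB has A in positions 1, 4, 5 and 9, so it holds 4 A and 6 B.

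**Reading 1: the printed string is reused.** Nine copies give 36 A and 54 B. The next six letters, ABBAAB, add 3 and 3. The total is 39/57 of 96. Power = Φ{δ/[σ√(1/a + 1/b)] − 1.96}:

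| Split | Before loss | After 5% loss |
|---|---|---|
| 48/48 | 82.2% | 80.2% |
| 39/57 | 80.8% | 78.8% |

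The cost is 1.4 points. On the noncentral t with an exact 40:60 split, power falls from 81.4% to 79.8% before loss and from 79.3% to 77.7% after, a cost of 1.6 points. Every allocation would be known to anyone who has the string.

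**Reading 2: balanced tens (5 A, 5 B).** The example is then wrong. For someone who knows the block length and sees past allocations:
- Mean number of allocations that are certain at the end of a block: 5/6 + 5/6 = 1.67 of 10.
- Mean number of correct guesses when always naming the arm with more places left: 5 + 2⁹/C(10,5) − 0.5 = 5 + 2.03 − 0.5 = 6.53 of 10. Enumerating all 252 orderings gives the same figure.

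As an illustration, assume that steering shifts a patient's expected bone loss by ±0.05 to ±0.15 mm according to the guess. The bias is 2 × shift × (2 × 0.653 − 1), or 0.03 to 0.09 mm, which is 15% to 46% of the 0.2 mm target. The shift is an assumption; the protocol gives no such figure.

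For balance, 96 units are nine full blocks plus six. The split is 48/48 with probability C(5,3)²/C(10,6) = 100/210 = 0.476, 47/49 in either direction with probability 0.476, and at worst 46/50.

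**Reading 3: tens drawn by simple randomisation.** A ten is 5/5 with probability 252/1024 = 0.246, so an unbalanced example is unremarkable. The expected split of 96 is 48/48. Exactly 48/48 has probability 0.081, and 39/57 or worse in either direction has probability 0.082. Past allocations reveal nothing, and grouping by ten serves no purpose.

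**The case against.** A reader might infer that the scheme cannot give 48 per group. The text does not support that. The string is marked as an example, nothing says that it is the list in use or that it repeats, and other tens could offset it. Section 5.1 itself speaks of "an expected N of 48 per group", which is not a guaranteed count. This objection stands: the protocol fails to secure balance but does not rule it out.

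A reader might also treat imbalance and predictability as two defects of one scheme. They belong to different readings. The 65% guess rate needs balanced tens, which the example contradicts; an independently drawn ten cannot be guessed at all. The route to prediction is also partly unstated. The main researcher is named for the examination and imaging work-up, while recruitment and randomisation are described without an actor. Surgery comes only in the third session, so seeing the brand placed lags behind allocation. Eligibility and consent already precede randomisation. These points stand, and the predictability figures are therefore conditional.

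It could be said that the analysis deals with any selection. Section 5.8 compares implants A and B by multiple linear regression that controls for smoking, cigarettes per day, jaw and ISQ, among others, so steering on those factors would be partly adjusted for. It does not list oral hygiene, bruxism or clinical impression. Regression does not replace concealment.

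Finally, the power loss is small. If 5.1's hope of 100 implants per arm were met and implants were independent, an 80/120 split would still have about 98% power (normal approximation). That stands too.

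**Conclusion.** The point holds in limited form. Section 5.5.1 states an allocation method whose only illustration is unbalanced, in a protocol that plans 48 per group. It leaves open whether tens are balanced, whether the unit is the patient or the implant, and who holds the list. Each of the three readings needs correction: reuse gives 39/57 and full predictability; balanced tens make the example wrong and disclose a fixed block length; independent tens do not secure balance.

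Concealment and the unit are the main issues. Power is minor, at 1.4 to 1.6 points and only if the string is reused. A reader might infer that imbalance is what takes power below 80%. The figures do not show this: on the t distribution the equal split is already at 79.3% after the planned 5% loss, and which side of 80% the other figures fall on depends on the approximation and on whether losses are counted.

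The guess rate of about 65%, with 1.7 of 10 certain, rests on balanced tens, a known block length and sight of past allocations. None of these is established by the text. What is established is that the method as written does not prevent them.

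**What to change.** In 5.5.1, replace the printed example with computer-generated permuted blocks holding equal numbers of A and B, with block sizes that vary at random and are not disclosed in the protocol. Name the patient as the unit of randomisation, state that all of a patient's study implants follow that allocation, and bring the counts in 5.1 and 5.7 into line. Have the list or sealed envelopes held by an existing department member who neither recruits nor operates. Keep the order already stated, with eligibility and consent before allocation.

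The cost is a new list and a few sentences. The arms may end a few patients apart if recruitment stops within a block; even balanced tens would not guarantee 48/48, because 96 is not a multiple of 10. The regression in 5.8 can stay as planned, as a complement to concealment.
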